### I. Research Title:

Piloting the IPROACTIF program to preserve functioning and prevent cognitive decline

#### D. List all co-investigators and key research personnel on [Appendix P](#) and upload with this application packet.

### III. Performance Sites

**Definition of a Performance Site:** A performance site is a location at which the research is conducted, data is gathered from subjects and/or records, and/or subjects are consented into the research. Sites are performance sites whether the research activities there are funded or not funded.

**A. Are there non-UIC performance sites?**

No – *Skip to Section IV.*  
 Yes – Complete [Appendix K](#) and upload with this application packet

---

## IV. Research Funding

**A. Is this research funded?**

No – *Skip to Section V.*  
 Yes  
 Pending

**B. Check all of the appropriate boxes for funding sources (including pending sources) for this research. If the study is supported by more than one funding source, complete and upload [Appendix Z](#) for each additional funding source.**

Federal Agency Name: **National Institutes of Health**  
 Foundation Name:  
 State Agency Name:  
 Department of Defense – Complete [Appendix Q](#) and upload with this application packet  
 Sub-contract from non-UIC agency or institution: Name:  
 Other - Name:

**C. Funding Identification:**

1. Institutional Proposal (IP) Number: **0045807**
2. a. Name of the PI on the grant or contract received directly from the sponsor: **[name]**  
b. Is the PI of this grant or contract affiliated with UIC?  
 No – Identify the agency or institution with which the above PI is affiliated:  
Explain the relationship between that agency or institution and UIC:  
 Yes
- c. Grant, contract or sub-contract title: **Midwest Roybal Center for Health Promotion and Translation**
- d. Grant, contract or sub-contract number: **5P30AG022849-17**

---

## V. Conflict of Interest (COI)

All investigators must disclose all real, apparent, or potential Significant Financial Interest (SFI) to the IRB. For more information, see the [Investigator Conflict of Interest Disclosure Policy for Human Subjects Research](#).

**A. Disclosure**

1. At present or in the 12 months prior to this disclosure, did or does any investigator or investigator's family members have a significant financial interest (SFI) with the research sponsor or any subcontract recipient; or have a SFI reasonably related to a product (e.g., drug, device, method, treatment, etc.) that is the subject of the research; or have any other relationships (e.g. fiduciary, even if uncompensated) that may present a potential conflict of interest with this research?  
 No  
 Yes – See Section B below.
2. Are you aware of an institutional conflict of interest with this study?

No  
 Yes – See Section B below.

## B. Management

If **YES** is checked for any of these questions, complete the disclosure and management plan via START myDisclosures application (<https://myresearch.uillinois.edu/myDisclosures/>). Guidance can be found on the [COI website](#) under “Managing Conflicts”. Final IRB approval of the research cannot be provided until a management plan is in place and is approved by the IRB. For additional assistance contact the COI Office at **[contact] / [contact]** or email [[contact]](mailto:[contact]).

---

## VI. Protocol Components

- A. Provide a description of the background and rationale for the proposed research. Cite appropriate literature to support the relevance and importance of this research.
- B. State the research objectives/hypothesis being explored by the current research. Please include primary and secondary aims.

**Chronic conditions such as diabetes and heart disease entail cardiovascular risk factors which play a critical role in cognitive decline. The majority of aging adults presenting with these conditions and associated cardiovascular risk factors such as obesity, hyperlipidemia, hypertension, and physical inactivity, are treated in primary care settings. Thus, primary care offers an opportunity to help patients manage chronic conditions, modify cardiovascular risk factors, and prevent cognitive decline. One promising way to identify and target at-risk patients in primary care settings is through focus on activities and instrumental activities of daily living (ADLs and IADLs).**

Primary care patients with chronic disease(s) and cardiovascular risk factors are more likely to be in the stage of preclinical cognitive changes. Converging evidence indicates that subtle deficits in ADL and IADL performance precede clinically identifiable cognitive impairment. ADL limitations are also strong predictors of progression between normal cognition, mild cognitive impairment (MCI), and dementia. Evaluation and rehabilitation of ADL/IADL performance in at-risk patients can activate a positive cycle of ADL independence, better management of chronic disease, lowering of cardiovascular risk factors, and prevention/deceleration of cognitive decline. However, there is a dearth of evidence-based interventions that focus on ADL/IADL training for at-risk aging patients in primary care.

- C. Clearly describe the study design/intervention. The description should demonstrate how the stated objectives will be met.

**IPROACTIF (Integrated PRimary Care and Occupational Therapy for Aging and Chronic Disease Treatment to preserve Independence and Functioning) is an intervention designed to be delivered in primary care settings by an on-site occupational therapist. Based on the premise of preventing the physical and cognitive decline that is associated with aging and chronic disease, the 12-week intervention includes a comprehensive assessment of ADL functioning and ten intervention sessions**

- **In-person assessments – A week to ten days after the phone surveys, participants will be asked to visit the study occupational therapist at the faculty practice clinic at 1640**

**[name] or in the Department of Occupational Therapy, 3rd floor, [name]. During this visit, the therapist will assess their physical and mental functioning using a variety of standard tests. The therapist will also give each participant an accelerometer to take home and teach them how to wear it.**

- **Video/Phone call assessment – A week after the in-person visit, the therapist will make an appointment for a video/phone call with each participant. During the video/phone call, the therapist will observe the participant performing one or two daily living tasks in their home.**

- **Wearing the accelerometer – During the week between the in-person visit and the video/phone call, we will ask participants to wear the accelerometer for at least 12 hours a day for 7 days. The accelerometer along with a stamped and self-addressed return envelope will be provided to the participant at the end of their in-person visit.**

**During this visit, the therapist will explain the purpose of the accelerometer and demonstrate how to wear it. The participant will be informed that a research assistant will contact them by**

**phone after a week to check if they are wearing the accelerometer and answer any questions. If participants have completed their 7-day data collection period, they will be asked to return the accelerometer using the envelope provided. If not, they will be instructed to start wearing the accelerometer at their earliest convenience. A research assistant will check on the participant by phone again after a week. If the participant has still not begun wearing the accelerometer they will be reminded to do so at their earliest. After another week, a final reminder call will be made, and if the participant does not intend to wear the accelerometer, they will be asked to return it using the envelope provided.**

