#### **Follow-up Surveys and Assessments**

Twelve weeks after beginning the study, all participants will complete the same surveys and assessments completed during the beginning of the study. These surveys and assessments will be completed in the same order and using the same format as at the beginning of the study. Participants in the treatment group we will also complete a brief satisfaction survey.

**In addition, we will also record blood pressure and HBA1C readings from participants' medical records AFTER we have obtained consent from participants. For participants in the treatment group, we will use readings from their last visit with the PCP before the intervention and closest visit with the PCP after the intervention. For participants in the control group, we will use the information that is available in their medical records from the last available record before the date of completing the baseline surveys and assessments, and the next available record approximately 10 weeks after the date that they complete the baseline surveys and assessments.**

**Two occupational therapists will also be involved in the study and will provide the aforementioned intervention sessions to all patient participants. Some of these sessions might be monitored (observed in real-time) by the PI or a research assistant as part of fidelity monitoring**

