## **VII. Research Records**

**A. Indicate the type(s) of data being collected and/or recorded (check all that apply):**

Interviews/Questionnaires

Audio recordings

Video recordings

Photographs

School/Student records

Internet research data

Lab, pathology and/or radiology results

University of Illinois Hospital & Health System medical records – University of Illinois Hospital & Health System medical records (only HBA1c and

Systolic/Diastolic blood pressure readings from last visit with PCP before the

intervention and closest visit with the PCP after the intervention – patients will NOT be asked to make an appointment just for the study. For participants in the control group, we will use the information that is available in their medical records from the

Initial Review Application: Social, Behavioral, and Educational Research, Version 5.2  
 last available record before the date that they completed the baseline surveys and assessments, and the next available record approximately 10 weeks after the date that they complete the baseline surveys and assessments. For participants in both groups these data will be abstracted AFTER consent is obtained.

Physician/clinic/hospital medical records from sources outside of UI Health System  
 Psychotherapy Notes

Billing records

Data previously collected for research purposes

Data containing no health information

Study-generated health information

Biological specimens

X Other. Describe: **Performance-based observations by a clinician**

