**UIC**

Initial Review Application: Social, Behavioral, and Educational Research, Version 5.2  
*student records) and upload with this application packet*

Decisionally-Impaired - *Complete Appendix V and upload with this application packet*

Economically and/or Educationally Disadvantaged

Vulnerable to Coercion or Undue Influence

Other: specify

**C.** If including economically and/or educationally disadvantaged subjects, subjects vulnerable to coercion or undue influence, UIC Employees, and/or other populations that may be considered vulnerable, provide a rationale for their inclusion and what additional safeguards, if any, are in place to protect their rights and welfare:

**Two UI Health clinicians will be included in the study as the lead interventionists. They will provide data about the treatment sessions, which is necessary to monitor the fidelity of the experimental intervention. Specifically, the PI or a research assistant will attend and observe randomly selected treatment sessions and will complete a fidelity monitoring checklist based on their observations of the clinician's delivery of the session (uploaded). Clinicians will also be asked to complete case notes for each treatment session. The case notes template is embedded in the intervention manual.**

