**To reduce this risk, patient participants will be told that being in the study is completely voluntary. They can choose to not participate in the study and they can discontinue their participation at any time. They will be told that choosing to not be in the study will not affect their legal rights, access to health care, or the quality of health care that they receive at the study clinic. All study-related compensation (\$25-\$75) has been kept to a reasonable amount so as not to make patients feel compelled to participate. Efforts will be made to ensure that participants consent to becoming involved in the project only after gaining a clear understanding of the study procedures and their rights as research participants.**

**The clinicians who will be serving as interventionists in the study also work at two of the clinics where recruitment will be conducted. It must be noted that both clinicians are co-investigators on the study and clinical faculty in the Department of Occupational Therapy. Neither their clinical contracts nor their academic appointments are contingent on the success of this study. In other words, there is no monetary reward or incentive for recruiting patients into the study.**

**The following steps will also be taken to minimize coercion during patient recruitment. These steps pertain to all healthcare providers who will assist with recruitment including, but not limited to, the study interventionists:**

1. Providers will be advised to bring up the topic of this research only at the end of their clinical consultation to ensure that the patient's therapeutic needs are not compromised.
2. Providers will be advised to remind patients that participation in the study is not obligated and should they decide to not participate, they will continue to receive their usual clinical care.
3. Providers will be advised to remind patients that they can take 2-3 days to reflect on the study before making their decision.
4. It must be noted that providers will only seek patient permission to introduce them to the research assistant or pass on their contact information to the research team so they can receive a call from a research assistant to explain the study in detail. The actual decision to participate or not will be made during the in-person meeting or phone follow-up which will be conducted by a research assistant not connected with the patient's clinical care

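### The plan does not say who scores the therapist-rated follow-up tests or whether that person is masked, so a treating therapist may rate their own patients

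*Combined protocol and SAP*

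**What the plan says.** Section VI.D sets out two therapist-rated baseline assessments. At the clinic or department visit, "During this visit, the therapist will assess their physical and mental functioning using a variety of standard tests". About a week later, by video or phone, "the therapist will observe the participant performing one or two daily living tasks in their home". Randomisation follows these assessments.

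Under Follow-up Surveys and Assessments in VI.D, everyone repeats the battery twelve weeks after starting: "These surveys and assessments will be completed in the same order and using the same format as at the beginning of the study". That passage gives order and format but no rater. Section VII.A describes one type of study data as "Performance-based observations by a clinician". No supplied section mentions masking of assessors or keeps rating separate from treating.

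On staffing, the same part of VI.D says that two occupational therapists "will provide the aforementioned intervention sessions to all patient participants". Since VI.D also says that controls get no therapist sessions, I read this as all treated participants; the two statements should be reconciled. Section VIII.C adds that "Two UI Health clinicians will be included in the study as the lead interventionists", and IX.C that "both clinicians are co-investigators on the study". Controls have usual primary care (VI.C) and short weekly calls from a research assistant (VI.D).

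**The concern.** After about ten weeks of working with a participant on personal goals, a therapist knows the allocation and has a stake in that participant's progress. If the same therapist then scores observed performance, treated participants may be marked more favourably. Nothing comparable can happen for controls, so any such bias runs in one direction.

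Baseline is rated before allocation, so the bias would enter at follow-up only and pass straight into the change score. Section VI.E uses the between-group difference and effect size to plan the sample size of later trials. A systematic shift in that effect is not averaged out by more participants and cannot be corrected afterwards from the data collected.

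The point covers only the follow-up in-person tests and the home-task observation. The phone surveys, accelerometer data, and blood pressure and HbA1c from records are not described as therapist-scored.

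**Working it through.** **Who rates: the passages side by side**

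1. VI.D: a therapist performs both baseline assessments. Which therapist is not stated.
2. VI.D, follow-up: same assessments, order and format. A therapist rating again is the natural reading, but no person or role is given.
3. VI.D, VIII.C and IX.C: the therapists clearly described are the two interventionists.
4. VI.C: the comprehensive assessments are listed as components of the intervention, and the interventionist uses the results to set goals.
5. X.C: the account of how intervening clinicians handle fatigue refers to participants resting before the assessment resumes, which places those clinicians at assessments.

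Items 4 and 5 support an overlap of treating and rating. None of the five says that a therapist rates their own patients.

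**What a bias would do to the sizing of a later trial (illustration)**

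The documents give no bias, SD, correlation, target effect, power or allocation ratio. The enrolment of 75 (VIII.A) has no derivation, so it cannot be reproduced; it is used here only for the sampling margin.

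Assumptions: two equal arms, two-sided 5% test of change between arms, 80% power, and a later trial planned on the biased pilot effect but free of that bias itself. Effects are in SDs of the change score. A shift of b SDs of a single score equals d = b/√(2(1−r)) SDs of change, where r is the pre-post correlation. At r = 0.5, d = b. A shift of 0.2 becomes 0.17 at r = 0.3 and 0.26 at r = 0.7.

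The projected n per arm is the smallest n with 80% power at (true effect + bias), from the noncentral t with 2n − 2 df and noncentrality effect × √(n/2). True power is then evaluated at the true effect. For example, with true effect 0.3 and bias 0.2, the apparent effect is 0.5 and n = 64. At the true effect the noncentrality is 0.3 × √32 = 1.70 and power is 39%.

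| Bias (SD) | True effect 0.3: n, true power | True effect 0.4 | True effect 0.5 |
|---|---|---|---|
| 0 | 176, 80% | 100, 80% | 64, 80% |
| 0.1 | 100, 56% | 64, 61% | 45, 65% |
| 0.2 | 64, 39% | 45, 47% | 34, 53% |
| 0.3 | 45, 29% | 34, 37% | 26, 42% |

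If the bias comes only from having treated the participant, and half of the treated participants are rated by their own therapist, a 0.2 SD bias averages 0.5 × 0.2 = 0.1 SD, which is the second row.

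**For scale: the pilot's random error.** With 37 per arm (75 split equally, no dropout), the 95% margin on the standardised difference is t(0.975, 72) × √(2/37) = 1.993 × 0.2325 = ±0.46 SD, near zero effect.

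**The case against.** The strongest reply is that the text does not establish self-rating. VI.D refers to the study occupational therapist in the singular when describing assessment. It then says that two therapists are *also* involved to give sessions, which can be read as additional people. The form asks applicants to "List all co-investigators and key research personnel on" an appendix (Appendix P) that was not available, and it may list a separate assessor. X.A says that the clinician participants supply only fidelity data, although that describes them as research subjects and does not identify the rater. This stands: a reader might infer that therapists do score their own treated patients, but the documents support only that they may. Some cross-rating could already be intended.

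A second reply is that the illustration rests on assumed bias, that one uniform bias is applied to tests needing different amounts of judgement, and that the pilot's ±0.46 SD margin exceeds every bias assumed. This also stands as to size. It does not remove the point, because the margin is random and falls either way, whereas the bias has one direction.

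A reader might also infer that the pilot's false-positive rate is inflated. VI.E plans paired tests within groups and names no between-group test for the pilot, so there is no stated error rate to inflate. The exposure is in the effect size carried forward.

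Finally, having another therapist assess touches the intervention, because VI.C counts the assessments as part of it. That is a real cost of one version of the remedy.

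**Conclusion.** The point holds as a gap in the plan: the follow-up rater of the therapist-scored measures is not identified, masking is not described, and the text as written permits a treating therapist to rate their own patients. Whether that would happen is unknown, and so is the size of any bias.

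The consequence is an effect size that may be too favourable for planning. Under the stated assumptions, a bias of 0.1 to 0.3 SD would leave a later trial with 29% to 65% true power instead of 80%, across true effects of 0.3 to 0.5 SD. Confidence is medium because Appendix P could settle the matter. The change is worth making before follow-up ratings begin, since the study could not undo the bias later.

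**What to change.** In the follow-up part of VI.D, name the role that performs the in-person tests and the home-task observation, and state that this person does not treat that participant and is not told the allocation.

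- **If Appendix P already lists a separate assessor:** name that role and its masking status. Nothing more is needed.
- **If not:** before randomisation, assign every participant in both arms at random to one of the two therapists as rater for baseline and follow-up. If the participant is allocated to treatment, the other therapist delivers the sessions. The same rater is then used at both time points, and the rater's identity does not reveal the arm. Withhold session notes from the rater at both storage steps in X.B, the temporary Box folder and the server folder. Flag any rating made by the treating therapist.

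**Cost.** No extra assessments, sessions or staff, but scheduling, handover and some administration; the documents give no workload, so capacity is an assumption. The interventionist would set goals from a colleague's recorded baseline, although VI.C treats those assessments as part of the intervention.

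**What remains.** Participants may disclose their arm, adaptations may be visible during the home observation, and the rater is still a co-investigator. Suppose a 0.2 SD bias arises whenever the rater knows the arm. If that happens in 25%, 50% or 75% of treated follow-ups, 0.05, 0.10 or 0.15 SD remains. If absence forces the treating therapist to rate 10%, that adds 0.10 × 0.2 × (1 − share already unmasked) = 0.015, 0.010 or 0.005 SD. If instead the bias arises only from having treated the participant, crossing removes it except for those absences: 0.10 × 0.2 = 0.02 SD. Either way the change reduces the risk without removing it.

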#### **Follow-up Surveys and Assessments**

Twelve weeks after beginning the study, all participants will complete the same surveys and assessments completed during the beginning of the study. These surveys and assessments will be completed in the same order and using the same format as at the beginning of the study. Participants in the treatment group we will also complete a brief satisfaction survey.

**In addition, we will also record blood pressure and HBA1C readings from participants' medical records AFTER we have obtained consent from participants. For participants in the treatment group, we will use readings from their last visit with the PCP before the intervention and closest visit with the PCP after the intervention. For participants in the control group, we will use the information that is available in their medical records from the last available record before the date of completing the baseline surveys and assessments, and the next available record approximately 10 weeks after the date that they complete the baseline surveys and assessments.**

**Two occupational therapists will also be involved in the study and will provide the aforementioned intervention sessions to all patient participants. Some of these sessions might be monitored (observed in real-time) by the PI or a research assistant as part of fidelity monitoring**

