**B. Data Security and Management Plan****1. Indicate the identifiable elements that will be collected and/or included in the research records.****Check all that apply**

X Names	 Social Security Numbers*	 Device identifiers/Serial numbers
X Phone numbers	 Medical record numbers	 Web URLs
X Street address	 Health plan numbers	 IP address numbers
X City or state	 Account numbers	 Biometric identifiers 
X Zip Code	 Fax numbers	 Vehicle ID numbers
X E-mail address	 License/Certificate numbers	 Facial Photos/Images

Financial account information (including student ID)

All elements of dates (except year) for dates directly related to an individual; and all ages over 89 and all elements of dates (including year) indicative of such age

Date of Birth

Identifiable UIC Student Records  University Identification Number (UIN)

X Any other unique identifier - Specify: HbA1c and Systolic/Diastolic blood

pressure readings AFTER obtaining consent from participants. For treatment group participants we will record these parameters from their last visit with PCP before the intervention and closest visit with the PCP after the intervention. For participants in the control group, we will use the information that is available in their medical records from the last available record before the date of completing the baseline surveys and assessments, and the next available record

approximately 10 weeks after the date that they complete the baseline surveys and assessments.

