### 3. Data Security

a. Describe how all types of data as selected above will be secured.

i.  Indirectly with a code linked to the identity of the subject.

Describe the coding method, specify who will have access to the code/master key, indicate where the key is stored, and explain how it will be protected against unauthorized access: **Participants who enroll in the study will be assigned a numeric code in the outcome database in RedCap i.e. outcome data from REDCap will be identified by a code. The master list including the participants' names, contact information, and corresponding numeric codes will be stored separately from the research data. The master list will be saved as a Microsoft Excel spreadsheet on the secure network server of the College of Applied Health Sciences. The file will be password protected and only the PI, [name] and key research personnel, will have access to the password. Hard copies of permission flyers completed by participants who are screened eligible and agree to be in the study will be stored in locked filing cabinets in the PI's locked research lab. Only the PI, [name] and key research personnel, will have access to the cabinet.**

PHI collected post enrollment and POST CONSENT will include the following variables – BP and HbA1c reading [for treatment group participants – at last visit with PCP before the intervention and closest visit with the PCP after the intervention. For control group participants - last time tested before completing the baseline surveys and assessments, and the next available record approximately 10 weeks.] These data will be stored in the RedCap outcome database where subjects will be identified by a code. Note that dates of readings will not be recorded. We will record these variables as 'preBP', 'postBP', 'preglucose' and 'postglucose'. After data collections is completed the coded outcomes data with identifiers removed will be exported from RedCap as a CSV or SPSS file. The coded dataset without identifiers will be stored on a lab computer at [name], which is part of the network server of the College of Applied Health Sciences.

ii.  x Directly, personal or private identifiers (identifiable elements) are maintained with the data.

Justify the inclusion of direct subject identifiers, and indicate who will have access to the data:

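### Blood pressure and HbA1c readings are picked by different rules in the two arms and undated, so the planned dataset cannot show whether pre-to-post intervals are comparable

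*Combined protocol and SAP*

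**What the plan says.** The selection rule appears in four places of the combined protocol and SAP: Section VI.D (Follow-up Surveys and Assessments), VII.A, XII.B.1 and XII.B.3.

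- **Treatment arm.** In VI.D, "we will use readings from their last visit with the PCP before the intervention and closest visit with the PCP after the intervention". Section XII.B.1 repeats it: "For treatment group participants we will record these parameters from their last visit with PCP before the intervention".
- **Control arm, pre reading.** Section VII.A takes the "last available record before the date that they completed the baseline surveys and assessments".
- **Control arm, post reading.** Section VI.D takes "the next available record approximately 10 weeks after the date that they complete the baseline surveys and assessments". Section XII.B.3 words the control pair as "last time tested before completing the baseline surveys and assessments, and the next available record approximately 10 weeks".
- **Visits.** Readings depend on routine care: "patients will NOT be asked to make an appointment just for the study" (VII.A).
- **Dates.** "Note that dates of readings will not be recorded" (XII.B.3). Only a pre and a post value are kept for blood pressure and for glucose.

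Everything else runs on one clock: "Twelve weeks after beginning the study, all participants will complete the same surveys and assessments completed during the beginning of the study" (VI.D).

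Section VI.E plans paired tests within each group. It also uses between-group differences, variability and effect size to project the sample size of later trials. It does not mention these two measures by name.

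**The concern.** A comparison of change between randomised arms is easiest to interpret when both arms are measured by the same rule. Here three things differ by arm: the event that anchors the reading, the type of record that qualifies, and the way the post reading is chosen. With reading dates left out, nobody working from the dataset can check whether these differences mattered.

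What is at stake is limited. The readings are stored in the outcome database, so they may enter the between-group estimates that Section VI.E uses for planning. A difference in interval between arms, or wide variation in interval within arms, could then affect a projected effect size or standard deviation unseen.

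**Working it through.** The plan gives no figure to reproduce here. The check sets the two rules on one time axis and asks how far apart their anchors lie.

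**Inputs**

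- Control anchors: baseline completion, and about 10 weeks later (VI.D).
- Sessions are weekly. VI.D has ten after randomisation, although its list ends with a Session 12. VI.C describes 12 weekly sessions with the assessments in Sessions 1 and 2, and elsewhere a 12-week programme of assessment plus ten sessions. One further sentence in VI.C has 12 treatment sessions after goal planning.
- Baseline: phone surveys, an in-person visit 7 to 10 days later, and a video or phone call 7 days after that (VI.D). Taking the phone surveys as study start (an assumption), baseline is complete at the earliest after 7 + 7 = 14 to 10 + 7 = 17 days, or 2.0 to 2.4 weeks.
- g = weeks from baseline completion to the first session. The plan does not give it; 0 to 2 is assumed.

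**Anchors in weeks, with 0 = baseline completion**

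| Reading of the intervention | Start | End | Span | Span minus control | Post anchor minus control |
|---|---|---|---|---|---|
| Control rule | 0 | 10 | 10 | – | – |
| A: ten sessions after randomisation | g | g + 9 | 9 | −1 | g − 1 |
| B: 12 sessions, assessments as Sessions 1 and 2 | −1 | 12 − 2 = 10 | 11 | +1 | 0 |
| C: 12 treatment sessions after goal planning | g | g + 11 | 11 | +1 | g + 1 |

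B takes Session 2 as the last baseline assessment (week 0) and Session 1 as one week earlier. For g = 0, 1, 2 the post-anchor difference is −1, 0, +1 under A and +1, +2, +3 under C.

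**Which readings fit the common follow-up?** Study week 12 falls at 12 − 2.4 = 9.6 to 12 − 2.0 = 10.0 on this axis.

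- A ends at 9 (g = 0) or 10 (g = 1), which fits to within about half a week. With g = 2 it ends at 11, study week 13.0 to 13.4, after follow-up is due.
- B ends at 10, study week 12.0 to 12.4, which fits to within about half a week.
- C ends at 11 to 13, study week 13.0 to 15.4, after follow-up is due.

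On the readings that fit, the nominal post anchors differ by −1 to 0 weeks.

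**Pre reading and randomisation.** Randomisation follows baseline completion (VI.D). Under A, a treatment pre reading may be taken at any time up to the first session, so it can fall after randomisation; a control pre reading cannot. Under B both pre anchors precede randomisation and differ by about one week.

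**Record source.** The treatment rule requires a visit with the primary care provider. The control rule accepts an available record, or in XII.B.3 the last time tested. Endocrinology is a recruiting clinic. Sections IX.A and IX.B list it in connection with primary care providers, but no section says whether its visits count for these readings.

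**Actual intervals.** Neither arm has a stated look-back or upper limit. Section VIII.D excludes patients with two years or more since their last appointment, which bounds the appointment but not the age of a reading. As an illustration, a control pre reading from a visit just under 2 × 365 = 730 days old gives a gap of about 730 + 70 = 800 days before any delay in the post reading. This width is possible in both arms and is not evidence of a difference between them.

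**The case against.** Controls have no intervention start or end, so some substitute anchor is needed, and 10 weeks plausibly mirrors ten weekly sessions. A treatment pre reading taken after randomisation but before the first session is still a pre-treatment value. The missing look-back and upper limit apply to both arms alike. The trial is a pilot capped at 75, these are opportunistic readings, and neither measure is named as primary. Dates could be abstracted again while the master list exists.

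Most of this stands, and it limits the point to modest size. It does not answer the core of it. Baseline completion is a date that every participant has, so arm-specific anchors are not necessary. Re-abstraction is not planned, and Section X.B has the files destroyed once data analysis is finished.

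A reader might infer more than the documents support:

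- **That the blood pressure and HbA1c comparison is biased.** The documents give no visit frequency and no sign that intervals differ by arm. Any bias may be zero.
- **That the anchors are up to three weeks apart.** This needs reading C with g = 2. The sentence behind C conflicts with the ten sessions stated elsewhere in VI.C and in VI.D, and with the week-12 follow-up.
- **That Endocrinology readings are usable for controls only.** Sections IX.A and IX.B suggest that the clinic may count as primary care. The wording is unclear, not exclusionary.

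**Conclusion.** The concern holds in a limited form. The selection rules differ by arm in anchor and in source wording, and the planned dataset contains nothing from which the intervals could be compared. These are stated rules, repeated in four sections, so following the plan as written produces the problem.

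The nominal difference is small: at most about one week between post anchors. This assumes weekly sessions, baseline completed 14 to 17 days after the phone surveys, and a first session within about a week of baseline completion. The actual difference in intervals, and any resulting bias in mmHg or HbA1c, cannot be computed from the documents. The surveys and assessments, which share one clock, are not affected. The point is worth correcting before records are abstracted, mainly because the correction is cheap.

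**What to change.** 1. Reconcile the session descriptions in VI.C and VI.D with one another and with the week-12 follow-up.
2. In VI.D, VII.A, XII.B.1 and XII.B.3, replace the arm-specific text with one rule and one record source for all participants. State whether Endocrinology visits qualify.
   - Pre: the most recent reading on or before baseline completion, so that every pre reading precedes randomisation.
   - Post: the first reading on or after one common target day counted from baseline completion, the day to be set once step 1 is done.
3. Store the number of days from baseline completion to each reading, in place of calendar dates.
4. Report intervals and missing readings by arm. In a sensitivity analysis, restrict to a stated range of intervals or adjust for interval. Keep readings outside that range in the main analysis, since a pilot of at most 75 with no study-arranged visits can ill afford to discard them.

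The cost is up to four elapsed-day fields in REDCap (pre and post for each of two measures), wording changes in four sections, and a revision of the statement on dates in XII.B.3. One downside remains: a fixed target day may come before the last session if sessions slip. The stored days will show when a reading was taken relative to baseline, but not whether treatment had finished by then.
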